9.3 Statistical Analyses

9.3.1 General Considerations

Descriptive and summary statistics will be performed, as appropriate. Statistics will include number of observations, mean, standard deviation, median, range, and inter-quartile range for continuous variables, and the number and percent for categorical variables; 95% or 90% confidence intervals will be presented where appropriate. Additional statistics such as geometric mean and coefficient of variation (CV%) may be calculated as warranted. Demographics and baseline characteristics (e.g., age, sex, race, ethnicity, body weight) will be summarized using descriptive statistics.

The reasons for all discontinuations will be tabulated and grouped by treatment group and major reason. All deviations related to study inclusion or exclusion criteria, conduct of the study, subject management, or subject assessment will be described.

9.3.2 Primary Endpoint Analysis

The primary objective is to compare bioavailability under fasted vs. fed administration conditions, as measured by PK parameters of MDMA and its active metabolite MDA. These relationships will be sought using linear and nonlinear models.

Plasma PK parameters for MDMA and its active metabolite will be calculated using non-compartmental and/or compartmental methods as appropriate using actual sample collection times post-dose. Individual subject PK parameters will be listed and descriptive statistics will be

calculated for both cohorts. Mean and individual subject plasma concentration-time profiles will be presented on rectilinear and semi-logarithmic scales.

Plasma concentrations of MDMA and its active metabolite MDA will be listed for each individual subject and descriptive statistics will be presented for each time point. As warranted, PK data will be presented in tables and graphical displays with time “0” assigned to the dosing time of each treatment.

The statistical analysis will be performed on log-transformed peak MDMA concentrations (C_{max}), time to peak concentration of the drug (T_{max}), delay in achieving T_{max} (t_{lag}), terminal elimination half-life of the drug ($t_{1/2}$), apparent clearance (Cl/F), apparent volume of distribution (Vd/F), area under the concentration-time curve from dosing time to last measurement time (AUC_{0-t}) and area under the concentration-time curve from dosing time to infinity ($AUC_{0-\infty}$). The 90% confidence interval (CI) for the ratio of population geometric means between fasted and fed conditions will also be provided for C_{max} , AUC_{0-t} and $AUC_{0-\infty}$. The same analysis will be performed for the active metabolite MDA. An absence of a food effect on bioavailability is established if the 90% CI for the ratio of the population geometric means between fed and fasted treatments, based on log-transformed data, is contained in the equivalence limits of 80-125 percent for $AUC_{0-\infty}$ (AUC_{0-t} when appropriate) and C_{max} .

Correlations between PK parameters and safety may be explored graphically and if relationships are observed, exploratory analyses may be performed. Additional exploratory analyses may be conducted and will be described in detail in a separate analysis plan.

9.3.3 Safety Analyses

Safety and tolerability will be evaluated. Safety analyses include change from Baseline blood pressure, pulse, and temperature values at specified time points. All laboratory results and vital sign measurements will be summarized using appropriate descriptive statistics.

Adverse event (AE) data will be descriptively evaluated. Descriptive statistics (e.g., number of observations, means, standard deviations, medians, maximum and minimum values) will be used to summarize continuous variables. Frequencies, proportions, and the exact 95% confidence intervals (CI), when appropriate, will be used to summarize categorical variables. Subject listings will also be provided.

Suicidal ideation and behavior will be summarized according to suggestions made in the C-SSRS Scoring and Data Analysis Guide. The number and percent of positive responses of Positive Ideation, Serious Ideation, and Positive Behavior will be tabulated by treatment group and time period (lifetime, screening, baseline, each Dosing Session (pre- and post-IMP), Integrative Sessions, and endpoints). Frequency and incidence of positive or serious ideation and suicidal behavior will be presented using descriptive statistics in tabular format.

ECG analysis: Mean of the triplicate ECGs at each nominal time point will be used for all reporting and analysis; however, individual values will be used to calculate the correction coefficient (γ) for the individual correction QTc (QTcI). Individual correction coefficient, γ , will be estimated using linear regression of log QT on log RR for each subject using all baseline ECG assessments collected before Day 1 dosing within a subject.

The QTc corrections will be individual correction by QTcI = QT/RR^γ , Fridericia's by QTcF = $QT/RR^{0.33}$, and Bazett's by QTcB = $QT/RR^{0.5}$.

Change from baseline ($\Delta QTcI$) will be calculated as the average of the three predose assessments on Day 1 subtracted from the value (i.e., QTc) on Day 1 at a given time t . The effect of MDMA on cardiac repolarization will be assessed, as measured by the time point with the largest upper one-sided 95% confidence limit for the $\Delta QTcI$. The relationship between $\Delta QTcI$ (dependent variable) and MDMA or MDA concentrations (independent variable) will be determined using a linear mixed-effects model.

Additional safety analyses other than those described in this section may be performed if deemed appropriate and will be described in detail in a separate analysis plan.

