2.3.1 Risk Assessment

Potential risks, summaries, rationale, and mitigation strategy can be found in [Table 1: Risk Assessments](#). For more information, see Investigator’s Brochure, section 7.4 Risk Assessment and Mitigation.

Table 1: Risk Assessments

Potential Risk of Clinical Significance	Summary of Data/Rationale for Risk	Mitigation Strategy
Risk of IMP		
Cardiovascular and Cerebrovascular Events	MDMA transiently increases heart rate and blood pressure in a dose-dependent manner that is generally not problematic for physically healthy individuals. These changes typically last no more than 8 hours. Most people do not experience elevations in cardiovascular parameters that exceed those seen after moderate exercise. An examination of safety data drawn from Phase 2 and Phase 3 studies of MDMA-assisted therapy detected a dose-dependent increase in SBP and to a lesser extent DBP. Characterization of sympathomimetic effects among participants with controlled hypertension is ongoing.	
 • Triplicate ECGs and a 1-minute rhythm strip will be completed at screening to assess for undiagnosed cardiac conduction abnormalities. • Before and after IMP administration, site staff will monitor vital signs and perform triplicate ECGs. Site staff will attend to clinical signs and symptoms of potential rare complications of the cardiovascular effects of MDMA, such as stroke or acute myocardial infarction (AMI) after IMP administration. Any symptoms such as chest pain, shortness of breath, neurological deficit or confusion or other potential indicators of end organ effects will prompt additional vital sign measurements, and intervention if appropriate. Site staff will notify the investigator for evaluation if this occurs, see Section 7.1.1 QTc Stopping Criteria.

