4.2 Scientific Rationale for Study Design

This protocol is for a Phase 1 open-label study with a primary purpose of evaluating the effect of food on the pharmacokinetics of MDMA and its active metabolite MDA.

In addition, an increase in heart rate is anticipated following MDMA administration. Therefore, the secondary purpose of this study is to evaluate the effect of food on the safety and tolerability of oral MDMA, as well as MDMA effects on ECG.

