8.3.1.1 Check-in to CRU

Participants will arrive at the CRU the night prior to IMP administration.

- The site team will ensure the participant fasts for at least 10 hours prior to IMP administration and agrees to comply with all other requirements per [Section 5.3 Lifestyle Considerations](#).
- The site team will inquire about any possible changes in health and concomitant medications to ensure the participant continues to meet all eligibility requirements and record AEs, as described in [Section 8.7.5 Method of Detecting AEs and SAEs](#).
- The site team will complete symptom-directed physical exam, urine drug screen, urine nicotine/cotinine screen, alcohol screen, pregnancy test (for PABP only), and concomitant medication review.
- The site team will measure blood pressure, body temperature, and pulse.
- The site team will administer Since Last Visit C-SSRS.
- A symptom-directed physical examination, or additional vital signs measurements, may be conducted at any time if clinically indicated.

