8.3.1.2 Pre-IMP administration

Prior to each Dosing Session:

- The site team will inquire about any possible changes in health and concomitant medications to ensure the participant continues to meet all eligibility requirements and record AEs, as described in [Section 8.7.5 Method of Detecting AEs and SAEs](#).
- The site team will review procedures for the Dosing Session with the participant and some of the commonly experienced effects of MDMA.
- The site team will administer Since Last Visit C-SSRS.
- Ninety minutes to two hours prior to IMP administration, the site team will collect baseline measures:
 - Collect PK samples
 - Measure blood pressure, body temperature, and pulse
 - Administer a 12-lead ECG (in triplicate)
 - Administer the Subjective Effects VAS
- Thirty minutes prior to IMP administration, for Fed Treatments only:
 - Participants will begin eating a high-fat and high-calorie meal, see [Section 8.3.2 Pre-IMP Meal](#).

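### Both QT analyses rest on an individual correction exponent fitted to 6 (at most 9) scheduled resting drug-free ECGs per participant, which makes the QTcI result needlessly imprecise once MDMA raises heart rate

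*Protocol*

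**What the plan says.** Section 9.3.3 of the protocol (ECG analysis) fits the individual exponent by "linear regression of log QT on log RR for each subject using all baseline ECG assessments collected before Day 1 dosing within a subject". Triplicate means are used elsewhere, but for this fit "individual values will be used to calculate the correction coefficient". The effect on repolarization is then judged on ΔQTcI, "as measured by the time point with the largest upper one-sided 95% confidence limit", and the mixed model on MDMA or MDA concentration also takes ΔQTcI as its dependent variable. QTcF and QTcB are defined, but Section 9.3.3 assigns neither to a named analysis.

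The scheduled drug-free 12-lead ECGs are few:

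- **Screening:** Section 2.3.1, Table 1 states that "Triplicate ECGs and a 1-minute rhythm strip will be completed at screening".
- **Check-in:** Section 8.3.1.1 lists no ECG, only that "The site team will measure blood pressure, body temperature, and pulse".
- **Pre-dose:** Section 8.3.1.2 states "Ninety minutes to two hours prior to IMP administration, the site team will collect baseline measures", among them one triplicate 12-lead ECG per session.

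Section 8.6.4 has every ECG taken semi-supine after 5 minutes' rest. Section 4.2 states that "an increase in heart rate is anticipated following MDMA administration".

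**The concern.** An individual correction works only if the participant's own drug-free ECGs fix the slope of log QT on log RR. That takes many recordings over a range of heart rates similar to the range seen on drug. Here the slope comes from two or three resting occasions with nothing done to widen the RR range, and it is then used at heart rates the protocol expects to be higher.

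Within a participant the exponent error is the same at every post-dose time and scales with the change in log RR, so further post-dose ECGs do not average it out. If heart rate rises with concentration, the error also enters the concentration-QTc slope. At stake is the precision of the QT safety endpoint, the mean change from baseline in heart-rate-corrected QT.

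**Working it through.** The protocol gives no precision or power figure for the QT analysis, so there is none to reproduce.

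**Step 1: count the ECGs.** Before the first dose: 3 (screening) + 0 (check-in) + 3 (pre-dose) = 6 ECGs at 2 time points. With the second session's pre-dose triplicate: 6 + 3 = 9 at 3 time points. Section 9.3.3 allows either reading, because Section 8.3.5 gives each Dosing Session its own Day 1.

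**Step 2: effect of a given exponent error.** Assume a baseline of 65 bpm and QTc of 400 ms; neither is in the protocol. With error e in the exponent and no true QTc change,

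error in ΔQTcI ≈ 400 × (exp(e × ln(HR/65)) − 1).

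For e = 0.1:

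- 75 bpm: ln(75/65) = 0.143, giving 5.8 ms
- 85 bpm: ln(85/65) = 0.268, giving 10.9 ms
- 95 bpm: ln(95/65) = 0.379, giving 15.5 ms

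An exponent that is too small makes the error negative; one that is too large makes it positive.

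**Step 3: how large the exponent error is likely to be.** I simulated per-subject least squares of log QT on log RR, with a true exponent of 0.33 and true ΔQTc of zero, post-dose at 85 bpm. Assumptions: heart-rate SD of 3 to 5 bpm between occasions and 2 bpm within a triplicate; QT SD of 5 ms between occasions and 4 ms within. The share of the within-triplicate RR change that QT follows was set at 100%, 50% or 20%.

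| ECGs | SD of exponent | SD of ΔQTcI error per participant | Mean error, QT follows fully | Mean error, 50% | Mean error, 20% |
|---|---|---|---|---|---|
| 6 | 0.21 to 0.25 | 23 to 26 ms | about +1 ms | −6 to −9 ms | −10 to −14 ms |
| 9 | 0.14 to 0.18 | 15 to 19 ms | about +1 ms | −4 to −7 ms | −7 to −12 ms |

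A second simulation, with variances set directly on the log scale (log-RR SD 0.04 to 0.10 between time points), gave wider ranges at 85 bpm. The per-participant SD was 15 to 35 ms with 6 ECGs and 10 to 22 ms with 9. The mean error was 0 to +2 ms without RR error. With RR error that QT does not follow (SD 0.03), it was −6 to −15 ms with 6 ECGs and −4 to −14 ms with 9.

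**Step 4: carry this to the endpoint, which is a mean.** Section 9.5 gives at least 12 completers and 18 evaluable. Standard error from the correction alone:

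- n = 12: 15/√12 = 4.3 ms to 26/√12 = 7.5 ms
- n = 18: 15/√18 = 3.5 ms to 26/√18 = 6.1 ms

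At n = 12 the one-sided 95% multiplier is 1.796. The correction noise alone would therefore give a margin of 1.796 × 4.3 = 7.7 ms to 1.796 × 7.5 = 13.5 ms. It combines in quadrature with the other variability, so the net increase in the upper limit is smaller than that.

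**Step 5: compare a fixed exponent.** If true exponents vary between participants with an assumed SD of 0.05 around 0.33, QTcF has an error SD of about 5.4 ms per participant at 85 bpm. That is 5.4/√12 ≈ 1.6 ms on the mean, with bias near zero. If the population exponent is instead 0.05 away from 0.33, QTcF carries a bias of 400 × (exp(0.05 × 0.268) − 1) ≈ 5.4 ms, which does not shrink with sample size.

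**The case against.** The strongest case on the other side has five parts.

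- **Nine ECGs is at least as natural a reading as six.** This stands, and the ranges above cover both. Repeat or extra screening ECGs are possible, but none is scheduled.
- **The endpoint is a mean, so a per-participant SD overstates the problem.** This stands. The relevant figure is 4 to 8 ms at n = 12, which is still large beside about 1.6 ms for a fixed exponent.
- **The comparison favours Fridericia by construction, because the simulated true exponent is 0.33.** This also stands. It is why the possible bias of about 5 ms belongs in the account, and why a data-based sensitivity analysis is needed.
- **The ECG objective is described as supportive, and no pass/fail rule rests on QTcI.** Section 7.1.1 names QTcF for ECG review during the study, so that review does not depend on the fitted exponent. This lowers the priority but leaves a named safety endpoint tied to an imprecise correction.
- **Technical detail may be left to the SAP.** That does not answer the point, because Section 9.3.3 itself fixes the fitting method, its data and the two analyses that use it.

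A reader might infer that the planned analysis will hide QT prolongation. The documents do not support that. A downward bias needs QT to lag RR within triplicates, or some other RR error that QT does not follow, and no figure in the protocol bears on this. Without it the mean error is about zero, and the noise tends to raise the upper limit, which is the cautious direction.

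**Conclusion.** The point holds as one of precision and is worth fixing before QT results are seen. Section 9.3.3 ties both named QT analyses to exponents that the scheduled ECGs cannot estimate well. At an assumed rise from 65 to 85 bpm, the exponent SD is about 0.14 to 0.25 and the per-participant ΔQTcI error SD about 15 to 26 ms, or roughly 4 to 8 ms standard error on a mean of 12. The imprecision appeared in every scenario tried. A bias of about −5 to −15 ms is conditional on QT lag; without lag it is about 0 to +1 ms in the main simulation (up to +2 ms in the second). All millisecond figures rest on assumed heart rates and variances, since the protocol gives none. For a supportive safety objective in a food-effect study this is a should-fix: the primary PK comparison is untouched.

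**What to change.** In Section 9.3.3, and in the SAP to match:

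1. Make QTcF the main correction for the change-from-baseline analysis and for the concentration-QTc model.
2. Report QTcI as a sensitivity analysis, taking exponents from one mixed model of log QT on log RR that pools all participants' pre-dose ECGs from both sessions, so that individual slopes are shrunk towards the common one.
3. Plot QTc against RR for each correction.

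The cost is wording only. No new data are needed, QTcF is already computed, and the stated endpoint names no particular correction. The downside should be stated in the plan: a fixed exponent is not individualised, and it is biased by about 5 ms at +20 bpm if the population exponent differs from 0.33 by 0.05. The pooled-exponent analysis and the QTc-RR plots would help to reveal that.

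If the sponsor prefers to keep QTcI as the main correction, drug-free ECGs over a wider heart-rate range would have to be added. In simulation, 36 ECGs at 12 time points with log-RR SD 0.12 brought the per-participant error SD down to about 3 ms, but that means extra data collection.

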9.3.4 Other Analyses

Additional exploratory analyses will be outlined in the SAP.

9.4 Interim Analysis

An informal interim analysis may be conducted after 5 participants have completed at least one Dosing Session. This will allow for any issues with the pharmacokinetic assay to be identified as early as possible in the study.

ECGs may also be sent to the independent reviewer for analysis at this time, if requested by the sponsor.

9.5 Sample Size Determination

Approximately 50 participants will sign an ICF and be screened to achieve 24 enrolled, to yield 18 evaluable and at least 12 participants who complete both study periods. The sample size for this study is determined per FDA guidance on *Assessing the Effects of Food on Drugs in INDs and NDAs – Clinical Pharmacology Considerations*.

Note: Enrolled means a participant, or their legally acceptable representative, has agreed to participate in the clinical study following completion of the informed consent process and eligibility screening. Potential participants who are screened for the purpose of determining eligibility for the study, but do not participate in the study, are not considered enrolled, unless otherwise specified by the protocol. A participant will be considered as enrolled if the informed consent is not withdrawn prior to participating any study activity after screening.

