The washout period between Dosing Sessions will be at least 14 days. Participants that experience emesis within 4 hours after a drug dose may be withdrawn from the study and replaced with a new participant.

An End of Study Visit will be performed 2-10 days after the completion of the final Dosing Session.

An informal interim analysis may be performed after approximately 5 participants have completed at least one Dosing Session to confirm the PK parameters are reported as expected based on existing literature.

Number of Participants and Study Duration

Published trials in patient populations from the sponsor have a post-ICF ineligibility rate of ~62% for MDMA-assisted therapy. To ensure a healthy-control population, eligibility criteria are more narrow than those in patient population studies and therefore the sponsor anticipates a potentially higher screen fail rate. Therefore, the protocol will permit ICF and screening of up to 50

participants to achieve 12 participants enrolled to study intervention. If a participant withdraws prematurely, they may be replaced at the discretion of the study sponsor.

Study details include:

- The study duration will be approximately 10 weeks for each participant (including a screening period of 4 weeks).
- Two Dosing Sessions will occur, with a washout period of at least 14 days between treatments.
- Participants will stay at the Clinical Research Unit (CRU) starting the night prior to each Dosing Session and then remain in the CRU until 48 hours after dosing. An outpatient visit will occur 72 hours after dosing.
- After both Dosing Sessions have been completed, an End of Study Visit will occur 7-14 days after final Dosing Session visit.

Intervention Groups

Participants who are enrolled in the study will be randomized to 1 of 2 dosing regimens, both of which receive the same intervention in opposite order. Group 1 receives a Fasted Treatment followed by a Fed Treatment, while Group 2 receives a Fed Treatment followed by a Fasted Treatment.

Fasted Treatments: Following an overnight fast of at least 10 hours, participants will be administered 100 mg MDMA (equivalent to 120 mg MDMA HCl) with 240 mL of water. No food should be allowed for at least 4 hours post-dose.

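### The protocol gives two enrolment targets, 12 and 24, for the same 50 screened, and 24 does not follow from the only ineligibility rate it cites

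*Protocol*

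**What the plan says.** The synopsis (Section 1.1, Number of Participants and Study Duration) says that "the protocol will permit ICF and screening of up to 50" people, and gives the purpose as "to achieve 12 participants enrolled to study intervention". It supports the 50 with the sponsor's published patient trials, which "have a post-ICF ineligibility rate of ~62% for MDMA-assisted therapy", and adds that narrower criteria may push the screen-failure rate higher in this study. Replacement of early withdrawals is optional, at the sponsor's discretion.

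Section 9.5 uses the same screening number for a longer chain: "Approximately 50 participants will sign an ICF and be screened to achieve 24 enrolled, to yield 18 evaluable and at least 12 participants" who finish both periods. It cites FDA food-effect guidance as the basis for the sample size and gives no drop-out rate and no power calculation.

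Section 8.1.1 counts a participant as enrolled once eligible and randomized. Section 5.4.1 says that people terminated before their first dose are not evaluable.

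**The concern.** These two passages are the protocol's only statements of study size, and they differ by a factor of two. In the synopsis 12 is the number enrolled; in Section 9.5 it is the minimum number of completers. A site, an ethics committee or a reader of the final report cannot tell from the protocol whether 12 or 24 healthy volunteers are meant to be enrolled.

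Section 9.5 also promises a yield better than the protocol's own evidence. Getting 24 from 50 needs a lower screen-failure rate than the cited one, although the synopsis expects the rate, if anything, to be higher. If 24 is the real target, the synopsis limit on screening would probably be reached before enrolment is complete.

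**Working it through.** **Inputs.** Screened: 50 (a ceiling in the synopsis, an approximate number in Section 9.5). Enrolled: 12 (synopsis) or 24 (Section 9.5). Ineligibility after consent: about 62% (synopsis, from patient trials). The protocol gives no numerical rate for this study, so 65% and 70% below are assumptions that illustrate a higher rate.

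**Can definitions reconcile 12 and 24?** Suppose the synopsis figure means participants dosed and the Section 9.5 figure means participants randomized. Section 9.5 still needs 18 evaluable, and under Section 5.4.1 each of those must have been dosed. At least 18 dosed does not fit a target of 12, so the conflict remains.

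**Reproducing the plan's figure.** Expected enrolled = screened × (1 − ineligibility rate) = 50 × (1 − 0.62) = 50 × 0.38 = 19. The stated 24 is not reproduced; the gap is 5. Inflating 24 by the common shortcut, 24 × 1.62 = 38.9, or 39, does not give 50 either.

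**Rates implied by each pairing.** 24/50 = 48% eligible, so 52% ineligible, which is below the cited 62%. 12/50 = 24% eligible, so 76% ineligible, which is above 62% and in the direction that the synopsis anticipates.

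**Screening needed.** Enrolled ÷ (1 − rate): 24/0.38 = 63.2, so 64; 12/0.38 = 31.6, so 32.

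**Chance of reaching each target from 50.** Exact binomial tail, treating the 50 as independent with a common eligibility probability:

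| Ineligibility | Basis | Expected enrolled of 50 | P(at least 24) | P(at least 12) | Screened for 24 expected |
|---|---|---|---|---|---|
| 52% | implied by 24 of 50 | 24 | 0.555 | >0.999 | 50 |
| 62% | synopsis | 19 | 0.096 | 0.988 | 64 |
| 65% | assumed | 17.5 | 0.040 | 0.966 | 69 |
| 70% | assumed | 15 | 0.006 | 0.861 | 80 |
| 76% | implied by 12 of 50 | 12 | <0.001 | 0.554 | 100 |

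Screening 64 makes 24 only the expected yield. An 80% chance of at least 24 at 62% needs 71 screened.

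**The case against.** The strongest reply is that 62% is not this study's rate. It comes from patients screened for MDMA-assisted therapy, and Section 5.4 lets screen failures be rescreened, so 50 people need not mean 50 single attempts. Both facts stand, and for that reason 24 should be called unlikely at 62% rather than impossible. They do not rescue Section 9.5, because the synopsis uses the 62% to justify the 50, expects the rate to be possibly higher, and offers no lower figure.

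A second reply is that 24 might be 12 initial enrolments plus up to 12 replacements. Neither passage says so: Section 9.5 does not mention replacement, and the synopsis makes it discretionary. Even on that reading, 24 people would have to pass screening, so the yield problem is unchanged.

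Several stronger readings are tempting and are not supported:

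- A reader might infer that the floor of 12 completers will be missed, by scaling 24 down to 12 and applying that loss to 19. Section 9.5 gives 12 as a minimum, not as a forecast of 50% loss. From 19 enrolled, 12 completers needs 12/19 = 63% retention; at an assumed 75% retention the chance of 12 or more is 92%.
- A reader might infer a specific loss of power. The protocol gives no within-subject CV or expected ratio and sizes the study from guidance, so any power figure would measure the reader's assumptions.
- A reader might see 18 evaluable alongside 12 completers as an error. The PK analysis set in Section 9.2 does not require both periods, so the two numbers can coexist.
- A reader might infer that the ambiguous target, with the interim look, leaves the stopping point open. Section 9.4 describes an informal check for assay issues, with no stopping or resizing rule.

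**Conclusion.** The point holds in two parts. First, the enrolment target is contradictory, 12 against 24 for the same 50 screened, and this needs no assumption beyond the text. Second, the yield in Section 9.5 exceeds what the cited rate supports: 19 expected rather than 24, with about a 10% chance of reaching 24. The second part rests on applying the patient-trial rate to this study and on independent binomial screening outcomes; a higher rate, which the synopsis anticipates, makes the gap wider.

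The documents do not show which passage is in error. The synopsis pairing of 50 and 12 fits its own rationale better, but that does not establish the sponsor's intention.

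**What to change.** The sponsor should decide which enrolment figure is intended and write one chain (screened, enrolled, evaluable, completing both periods) identically in the synopsis and Section 9.5.

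- **If 24 is intended:** either restate screening as about 64 at 62% ineligibility, more if a higher rate is expected, and amend the synopsis cap of 50; or keep 50 and restate expected enrolment as about 19, with the evaluable number adjusted to match.
- **If 12 is intended:** correct the 24 and the 18 evaluable in Section 9.5, and say that obtaining 12 completers from 12 enrolled depends on replacing anyone lost. The 50 can stay, since 32 screened would be expected to give 12 at 62%, which leaves room for replacements.

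The cost is a wording amendment to two sections. Keeping 24 also means either a larger screening effort with a revised ceiling, or a less favourable stated yield.
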